1 BACKGROUND & STUDY SYNOPSIS

1.1 Background

Addressing Substance Misuse in HIV Service Settings

The significance of ending the HIV epidemic. In 2019, the Department of Health and Human Services launched the Ending the HIV Epidemic initiative with the goal of reducing new HIV infection rates by 90% through four key strategies: early diagnosis, rapid treatment to reach viral suppression, prevention, and outbreak response. Achieving this goal is possible with advances in antiretroviral therapies to treat and prevent HIV. Such therapies have significantly improved the quality of life and life expectancy of people with HIV (PWH) and have recently been shown to essentially eliminate the risk of transmitting HIV to sexual partners among PWH who maintain an undetectable viral load. Despite these advances, HIV incidence has remained steady since 2013, with approximately 39,000 new infections annually in the United States.¹ Consequently, HIV remains one of the most significant epidemics in the country, with 1.1 million PWH² and \$20 billion in annual direct health expenditures for prevention and care.³ With each new HIV infection having an estimated \$400,000 in public health costs, new HIV infections cost the nation approximately \$1.6 billion each year. *Innovative strategies that reach the hardest-to-reach populations with the highest rates of transmission will help the Ending the HIV Epidemic initiative achieve its goals.*

The significance of addressing substance misuse among PWH. One of the most significant barriers to ending the HIV epidemic is substance misuse among PWH (misuse of prescription medications, alcohol, or other drugs). Substance misuse among PWH has several adverse consequences that increase the risk of HIV transmission, including decreased adherence to HIV medications,⁴⁻⁷ poorer viral suppression,⁸⁻¹⁰ and increased incidence of risky sexual behaviors such as condom-less sex with partners who are HIV negative or who have an unknown status.^{11,12} Substance misuse rates are significantly higher among PWH than in the general population.¹³ Recently, Garner and colleagues (2019)¹⁴ found that use disorders for alcohol, opioid, and methamphetamine have the most significant population-level negative impacts for PWH. Few PWH access specialty substance misuse treatment services, even when available,^{15,16} highlighting the importance of improving care integration in HIV service settings. *If the Ending the HIV Epidemic initiative is to achieve its target of 95% of persons with diagnosed HIV infection achieving viral suppression, substance misuse among PWH must be addressed to help increase engagement in care and subsequently viral suppression.*

Despite the adverse impacts of substance misuse among PWH, research addressing substance misuse in HIV service settings has been limited,¹⁷⁻¹⁹ with most research to date addressing alcohol misuse in HIV primary care settings.^{17,19,20} [name] Abuse Treatment to HIV Care (SAT2HIV-I) Project (a dual-randomized, type 2 effectiveness-implementation hybrid trial) focused on HIV service organizations (HSOs) because they are well-positioned to address substance misuse among PWH given that (1) HSOs conduct assessments with clients twice per year, which provides opportunities to screen for and address substance misuse, and (2) relative to time-constrained HIV primary care settings, HSO case management staff

may be better able to make time for identifying and addressing substance misuse.^{21,22} We believe that to end the HIV epidemic in the United States, we must target missed opportunities to address substance misuse within HSOs. *Research that focuses on improving treatment for substance misuse within HSOs will have significant contributions to ending the HIV epidemic.*

The significance of integrating motivational interviewing-based brief interventions (MIBIs). Motivational interviewing²³ (MI) is effective for reducing substance misuse; it has more than 25 years of empirical support.²⁴⁻²⁷ However, MIBIs have only recently been examined in HIV service settings. Aharonovich and colleagues (2017)²⁸ found that compared with an educational control, MIBIs delivered in HIV primary care settings significantly decreased the frequency and quantity of non-injection drug use. Similarly, Satre and colleagues (2019)²⁹ found that MIBIs delivered in primary care settings decreased use of illegal drugs and misuse of prescription drugs. Most recently, Garner and colleagues (2019)³⁰ found that MIBIs delivered in HSOs significantly reduced substance misuse. *Thus, research supports the effectiveness of MIBIs for addressing substance misuse in HIV service settings.*

Testing Strategies for Implementation and Sustainment

The significance of testing different strategies using type 3 hybrid trial designs. The challenge of implementing evidence-based health interventions (EBHIs) in practice settings is well-documented,³¹⁻³⁵ with estimates suggesting it takes approximately 17 years for 14% of original research to reach patient care.³⁶ Implementation research aims to improve implementation of EBHIs through “the study of methods to promote the adoption and integration of evidence-based practices, interventions and policies into routine health care and public health settings.”³⁷ Although significant progress has been made, the field of implementation research remains in its infancy. Indeed, implementation research has succeeded in generating many models/frameworks,³⁸ as well as evidence to better understand key implementation barriers.³⁹⁻⁴¹ However, implementation research focused on the development and testing of strategies to effectively and cost-effectively address and overcome these barriers has been relatively limited. Additionally, Foy and colleagues (2015)⁴² have noted, “If studies evaluating the effects of implementation interventions are to be of relevance to policy and practice, they should have end-points related to evidence-based processes of care.” Thus, there is a significant need for implementation research that tests the effectiveness of implementation strategies in improving implementation outcomes and client outcomes, which Curran and colleagues (2012)⁴³ codified as hybrid trials. [name] SAT2HIV-I Project, funded by the National Institute on Drug Abuse (NIDA), addressed this need by using a dual-randomized type 2 hybrid trial design that simultaneously tested the effectiveness of a MIBI to reduce substance misuse and the effectiveness of an innovative implementation strategy called Implementation & Sustainment Facilitation (ISF).^{21,22} The SAT2HIV-II Project would address this need by using a type 3 effectiveness-implementation hybrid trial design to compare two strategies in terms of impact on implementation outcomes (primary aim) and client outcomes (secondary aim). This implementation research is especially critical in the context of major public health challenges such as substance misuse among PWH.

Consistent with NIH's encouragement to consider approaches previously used, we propose that the current control condition be the strategy found to be most effective as part of the SAT2HIV-I Project. Thus, the control condition will couple the staff-focused Addiction Technology Transfer Center (ATTC) strategy and the team-focused ISF strategy, which was found to be more effective than the ATTC strategy alone.³⁰ Consistent with the landmark research of Miller and colleagues (2004),⁴⁴ which provided the most rigorous support for the ATTC strategy in preparing staff to implement MIBIs, [name] and colleagues (2019)³⁰ found that ISF significantly improved implementation effectiveness (i.e., the *consistency and quality* of MIBI implementation). These results advanced implementation research on the effectiveness of facilitation (i.e., a process of interactive problem solving and support that occurs in a context of a recognized need for improvement and a supportive interpersonal relationship).⁴⁵⁻⁴⁸ Although ISF improved implementation effectiveness beyond the ATTC strategy, our results suggested that room for improvement remained, especially with regard to sustainment.³⁰ Indeed, even the ATTC+ISF strategy did not appear to be sufficient for MIBI sustainment, with only about one-third of HSOs reporting MIBI sustainment at follow-up. *Thus, we believe building on the promising results of the SAT2HIV-I Project is the next logical step in advancing this area of implementation research.*

The significance of testing Pay For Performance (P4P) as an effective adjunct to the ATTC+ISF strategy. P4P (i.e., providing monetary bonuses for achieving predefined performance targets) has been recommended as a promising strategy to improve the quality of care and address the research-to-practice gap.⁴⁹⁻⁵¹ In 2008, the National Institute on Alcohol Abuse and Alcoholism funded [name] and his research team to conduct a type 3 hybrid trial to test the effectiveness of using P4P to improve implementation outcomes and client outcomes within community-based substance use treatment organizations implementing an EBHI for adolescent substance use.⁵² More specifically, the P4P strategy was tested as an adjunct to a multifaceted strategy similar to the ATTC strategy.⁵³ As described by Garner and colleagues (2012),⁵⁴ P4P was found to have a significant impact on implementation outcomes and client outcomes. As such, we hypothesize that the P4P strategy (i.e., ATTC+ISF+P4P strategy) will improve implementation outcomes and client outcomes beyond the ATTC+ISF strategy. Additionally, we hypothesize that the P4P strategy will significantly improve sustainment by offering organizations monetary bonuses for developing a sustainment plan. *Thus, the proposed implementation research is significant because it will test the effectiveness of the P4P strategy as an adjunct to ATTC+ISF strategy, which may affect how the Health Resources and Services Administration (HRSA) funds the AIDS Education and Training Center (AETC) to support future HRSA-funded initiatives focused on improving the integration of MIBIs into HIV service settings.*

Identifying Implementation Strategies' Mechanisms of Change

Beyond understanding whether or not implementation strategies are effective, it is important that implementation research seeks to better understand *why* and *how* implementation strategies work (i.e., what the mechanisms of change are).⁵⁵ Thus, our research will seek to advance implementation research by examining the extent to which implementation climate (i.e., the extent to which the innovation is expected,

supported, and rewarded)⁵⁶ mediates the implementation condition to outcome relationship. We focus on implementation climate for several reasons. First, numerous implementation researchers have hypothesized implementation climate as the key construct that may explain the impact of implementation strategies on implementation effectiveness.⁵⁷⁻⁶¹ Second, implementation climate is one of the few constructs that has a psychometrically sound and pragmatic measure available.⁶² Third and most importantly, the P4P strategy is specifically designed to enhance the dimension of implementation climate that may not be addressed by the ISF strategy (i.e., reward). *Thus, this exploratory aim will help advance knowledge by improving understanding regarding the extent to which implementation climate is a key mechanism of change.*

Public Health Relevance

There is an urgent public health need to end the HIV epidemic and more broadly to identify effective strategies to overcome (not just understand) barriers to implementing and sustaining EBHIs in practice settings. The proposed MIBI for substance misuse has been shown to be effective for reducing substance misuse. Additionally, the ATTC+ISF strategy has been shown to be an effective strategy for implementing this MIBI within HSOs. However, even with the ATTC+ISF strategy, room for improvement remains, especially regarding sustainment. Given P4P has been shown to be highly effective, it may be an effective adjunct to the ATTC+ISF strategy (i.e., ATTC+ISF+P4P strategy > ATTC+ISF strategy). However, due to the strength of the research design (i.e., a 30-site, cluster-randomized, type 3 hybrid trial), we believe implementation research will be advanced significantly even if our hypothesis is not supported (i.e., if the ATTC+ISF+P4P strategy is not able to significantly improve implementation outcomes or client outcomes beyond the ATTC+ISF strategy).

1.2 Study synopsis

The SAT2HIV-II Project is a prospective 30-site cluster-randomized type 3 hybrid trial that is regulated by the Department of Health and Human Services and focused on testing the effectiveness of a Pay For Performance (P4P) strategy as an adjunct to the multifaceted ATTC+ISF strategy, which Garner et al. (2020) found to be the most effective strategy for integrating a MIBI for substance misuse into HSOs. The control condition, which will be provided to all participating HSOs, consists of the following for MIBI staff: 1) a 5-hour online introduction to MI course, 2) three 4-hour virtual training workshops that are focused on the MIBI, 3) standardized feedback reports regarding the fidelity with which each MIBI was implemented, 4) monthly 30-60-minute virtual group consultation calls with an MI expert regarding how to improve fidelity, and 5) monthly 30-60-minute virtual ISF team meetings with an implementation expert. In addition to these strategies, MIBI staff at HSOs randomized to the experimental condition will have the opportunity to earn a \$10 bonus for each MIBI implemented, as well as an additional \$10 bonus for each MIBI that is rated as meeting or exceeding the quality benchmark (i.e., 80th percentile fidelity score from the SAT2HIV-I Project). For leadership staff at all participating HSOs regardless of condition, participation consists of monthly 30-60-minute virtual ISF team meetings with an implementation expert. Other procedures that are included for research purposes only are online surveys with consenting staff and client participants.

2 OBJECTIVES & OUTCOMES

2.1 Objectives

The objective of the SAT2HIV-II Project is to test the effectiveness of P4P in improving implementation, sustainment, and client outcomes. Specific aims and hypotheses are:

Primary aim: Test the impact of ATTC+ISF+P4P on *implementation outcomes*.

Primary hypothesis: Relative to ATTC+ISF, ATTC+ISF+P4P will achieve significant improvements in staff-level measures of MIBI implementation consistency, MIBI implementation quality, MIBI sustainment consistency, and MIBI sustainment quality.

Secondary aim: Test the impact of ATTC+ISF+P4P on *client outcomes*.

Secondary hypothesis: Relative to ATTC+ISF, ATTC+ISF+P4P will achieve significant reductions in client-level measures of substance use, anxiety symptoms, and depression symptoms.

Exploratory aim: Test the extent to which implementation climate mediates the implementation condition to outcome relationship.

Exploratory hypothesis: Implementation climate will partially mediate the relationship between implementation condition and each of the outcomes in the primary and secondary aims.

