2.2 Implementation outcomes

The SAT2HIV-II Project's four implementation outcomes are:

MIBI implementation consistency: The cumulative number of MIBIs that each MIBI staff member implemented during the implementation phase.

MIBI implementation quality: The cumulative sum quality score that each MIBI staff member demonstrated during the implementation phase. Each MIBI session will be rated using the Lyssn Platform and the Independent Tape Rater Scale.⁶³

MIBI sustainment consistency: The cumulative number of MIBIs that each MIBI staff member implemented during the sustainment phase.

MIBI sustainment quality: The cumulative sum quality score that each MIBI staff member demonstrated during the sustainment phase. Only the Lyssn Platform will be used to rate each MIBI session during the sustainment phase.

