10 DATA ANALYSIS PLAN

All analyses will follow the intent-to-treat principle and will be conducted using R, SAS, or Mplus. The distribution of each outcome will be examined before analysis. If a distribution exhibits sufficient nonnormality, we will consider other distributions as an alternative to the normal distribution. Doing so will yield more accurate standard errors and p-values. To assess whether distributional choices were appropriate, we will conduct residual diagnostics. Before fitting mixed effects regression models, we will examine variance partitioning between the levels. Intraclass correlations (ICCs) will be estimated and included in publications. Organized by aim, below are descriptions of the sample size, missing data, power, and analysis plan.

Primary Aim. Analyses on the impact of the P4P strategy (i.e., ATTC+ISF+P4P compared to ATTC+ISF) on staff-level outcomes will be analyzed using a three-level mixed-effects regression model (repeated-measures t nested in staff s nested in organization o) with an appropriate distributional assumption. The primary predictor will be the P4P indicator (an organization-level predictor), and its estimated effect is β_2 . Random intercepts β_{0so} will adjust for organization differences. Random slopes β_{1so} allow for change over time. The basic reduced form of the model is $y_{tso} = \beta_{0so} + \beta_{1so}Time + \beta_2P4P + \epsilon_{tso}$. This model will be generalized with a link function if the outcome y_{tso} is nonnormal. Model comparisons will be used to select an appropriate trajectory shape (e.g., linear, quadratic) for the *Time* variable. A sensitivity analysis will

be conducted for each outcome by adding potential staff-level confounders (e.g., sex, race) to the model.

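### Does a primary hypothesis with four unranked outcomes, and no stated alpha or success rule, inflate the chance of wrongly supporting P4P?

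*Combined protocol and SAP*

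**What the plan says.** Section 2.1 (Objectives) states a single primary hypothesis: "ATTC+ISF+P4P will achieve significant improvements in staff-level measures of MIBI implementation consistency, MIBI implementation quality, MIBI sustainment consistency, and MIBI sustainment quality". Section 2.2 introduces these with "The SAT2HIV-II Project's four implementation outcomes are" and gives them no order. Two are counts of sessions, one per phase. The other two are summed quality scores over sessions in the same phases; for the first phase the definition is "The cumulative sum quality score that each MIBI staff member demonstrated during the implementation phase".

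Section 10 (Data Analysis Plan) fits one mixed-effects model per outcome and takes the P4P coefficient as the effect of interest. It mentions p-values but gives no threshold, no sidedness and no multiplicity method. It announces that "Organized by aim, below are descriptions of the sample size, missing data, power, and analysis plan", yet no power statement follows from which an alpha could be read.

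Two places in section 1.1 bear on how a mixed result might be read. The paragraph on P4P adds "Additionally, we hypothesize that the P4P strategy will significantly improve sustainment" and gives the reason: bonuses to organizations for a sustainment plan. The Public Health Relevance text describes the hypothesis failing as P4P bringing no significant gain in implementation or client outcomes; it does not say how many outcomes must improve.

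**The concern.** Four tests with no declared error rate and no declared success rule leave room to choose the rule after the results are known. If two of the four outcomes were significant, the document would not say whether the primary hypothesis was supported, partly supported or not supported. The background text treats sustainment as something of a hypothesis in its own right, so a result in one phase only is foreseeable. If improvement on any single outcome were then presented as support for P4P, the chance of a false claim would exceed the level a reader would assume for one test.

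**Working it through.** **Inputs from the document.** Four outcomes joined by a conjunction (section 2.1); one P4P coefficient per outcome (section 10); 30 organizations (section 1.2). There is no stated alpha, power or error rate, so there is no figure of the plan's own to reproduce.

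**Inputs assumed.** Two-sided 0.05 per test with only improvement counting, so 2.5% per outcome; 15 organizations per arm; normal organization means compared by a pooled t test on 30 − 2 = 28 df. This illustrates the arithmetic and is not the three-level model of section 10. Within-phase correlation is taken as 0.84-0.99, because summed quality adds scores over the sessions that consistency counts. Correlation across phases is taken as 0.3-0.9. None of these values is in the document.

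**Step 1: all four required.** The hypothesis is false if at least one outcome has no benefit. Supporting it requires that outcome's test to be significant, so

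P(false support) ≤ P(that one test is significant) = 2.5%.

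This holds for any correlation. With no effect on any outcome the probability is lower still: 0.1-1.1% at within-phase correlations of 0.8-0.95 and cross-phase correlations of 0.3-0.9.

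**Step 2: any one sufficient (not a rule in the document).** With independent tests, 1 − (1 − 0.025)^4 = 1 − 0.9037 = 9.6%. With correlated outcomes and no effect on any of them, simulation gives:

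| Within phase / across phases | Any-one false support |
|---|---|
| 0.84 / 0.3 | 7.1% |
| 0.84 / 0.7 | 6.1% |
| 0.90 / 0.7 | 5.8% |
| 0.98 / 0.3 | 5.6% |
| 0.99 / 0.7 | 4.8% |
| 0.99 / 0.9 | 4.0% |

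Relative to 2.5% this is 4.0/2.5 = 1.6 to 7.1/2.5 = 2.8 times. A separate calculation at within-phase 0.8-0.95 and cross-phase 0.3-0.9 gives 4.4-7.3% from the normal distribution and 4.3-7.1% from the t distribution on 28 df.

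**Step 3: what a formal adjustment would buy.** Take an effect of 1.06 organization-level SDs, which gives noncentrality 1.06 × √(15/2) = 2.90 and 80% power per outcome at two-sided 0.05. Compare no adjustment with Hochberg's step-up procedure across the four tests:

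| Situation | Unadjusted | Hochberg |
|---|---|---|
| All four benefit: chance that all four are significant | 58-73% | identical |
| All four benefit: power per outcome | 80% | 72-74% |
| One phase benefits: power for an affected outcome | 80% | 62-63% |
| One phase benefits: false support in the other phase | 2.8-3.8% | 2.0-2.2% |

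For the hypothesis as worded, the adjustment changes nothing. In the one-phase case, which is the main reason to expect partial claims, it costs 17 to 18 points of power (80 − 63 and 80 − 62). False support falls by less than 2 points (3.8 − 2.0 = 1.8 at most).

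**The case for a change.** The strongest case for a change is that mixed results would be common. If P4P truly improved all four outcomes with 80% power each, some but not all would be significant in about 39% of trials at correlations 0.84/0.3, 27% at 0.90/0.7 and 13% at 0.99/0.9. The document gives no verdict for these cases. Its background text does not hold firmly to an all-four reading: sustainment appears as an added hypothesis, and the remark on what failure would look like could be taken to mean that some improvement is enough. Stating a rule would take only wording.

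The omission stands, and so do the frequencies under their assumptions. They do not show that the primary hypothesis, followed as written, gives a wrong conclusion: in each of these cases the four-part hypothesis is simply not met in full. The background passages explain motivation and mechanism and set no testing rule. Nor is there one correct repair. Requiring all four, ranking them, naming one as primary, reporting four labelled hypotheses, or applying Hochberg or Holm would each be defensible. The adjustments carry a real power cost in a trial described as a "prospective 30-site cluster-randomized type 3 hybrid trial".

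**Conclusion.** No change follows. The document does leave alpha, sidedness and the handling of partial results unstated. The conjunction in section 2.1 already supplies a rule under which false support is at most 2.5%, given the conventional two-sided 0.05 with only improvement counting. The 4-7% figure (9.6% at independence) belongs to an any-one rule that the document does not adopt, and it rests on an assumed alpha, allocation and correlations. What remains is a reporting gap that analysts can fill sensibly: give all four estimates with their intervals and p-values, and call the hypothesis supported only when all four improve. Whether to control error across partial claims as well is a fair trade-off between power and a modest reduction in false support. The conclusion would differ if the trial later claimed its primary hypothesis on the strength of one outcome, but nothing in the text commits it to that.
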